11.3.3. Best Overall Response

Best overall response (BOR) is defined as the best response as determined by the investigator, recorded between the date of randomization and the date of objectively documented progression per RECIST v1.1 or the date of subsequent therapy, whichever occurs first. For patients without documented progression or subsequent anti-cancer therapy, all available response assessments will contribute to the BOR determination. Complete or PRs may be claimed only if the criteria for each are met at a subsequent time point as specified in the protocol (approximately 4 weeks later).

For patients who continue pegilodecakin in combination with FOLFOX treatment beyond suspected pseudoprogression, if the pseudoprogression is not confirmed in the following scan, the additional responses occurred after the pseudoprogression should be considered in deriving BOR.

Confirmed responses are those that persist on repeat imaging study 4 weeks after initial documentation of response. Designation of best response of SD requires the criteria to be met at least 8 weeks (\pm 3 days) after randomization. Designation of best response of SD requires the criteria to be met at least 8 weeks (\pm 3 days) after randomization.

Best overall response will be summarized along with the exact 95% CI by randomized arm.

11.3.4. Subsequent Anti-Cancer Therapy

The number of patients starting a new anti-cancer therapy will also be summarized by treatment arm. The subsequent anti-cancer therapies will be coded by WHO Drug Dictionary and summarized by regimen.

11.3.5. Sensitivity Efficacy Analyses

The additional sensitivity analyses for OS includes:

OS sensitivity analysis 1: An overall survival analysis censoring patients at the time of initiation of subsequent anti-cancer therapy.

OS sensitivity analysis 2: An overall survival analysis defining OS time as the time from the date of study enrollment to the date of death due to study disease. Survival time will be censored on the date the patient was last known to be alive for patients who have no reported event. For patients that have died due to reasons which are not disease related, survival time will be censored at the date of death.

OS sensitivity analysis 3: OS will be analyzed after adjusting for selected prognostic factors. Potential prognostic factors include the stratification factors (per CRF) and other factors as outlined in Section 11.1.1. The HR for treatment effect will be estimated using a multivariate Cox proportional hazard model constructed by selecting variables among all the potential variables, using stepwise selection method with entry p-value 0.05 and exit p-value 0.01. The treatment factor will be kept out of the model throughout the covariate selection process and only added into the final model.

The additional sensitivity analysis for PFS includes:

PFS sensitivity analysis 1: A PFS analysis that considers clinical progressions as events.

PFS sensitivity analysis 2: A PFS analysis that does not censor for the start of additional anticancer therapy

PFS sensitivity analysis 3: A PFS analysis that considers pseudoprogression as events. For patients with multiple progression events, the PFS is defined as from the randomization to the first progression event.

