3.0 STUDY POPULATION

3.1 Patient Selection Criteria

Investigators will maintain a screening log of all potential study candidates that includes limited information about the potential candidate (eg, initials, age, and gender), date, and outcome of the screening process (eg, enrolled into study, reason for ineligibility, or refusal to participate).

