3.3 Rescreening Criteria

Re-screening may be allowed. Patients who are re-screened after 30 days must be re-consented with a new screening number and repeat the screening assessments. For patients re-screened within 30 days, assessments with results that would exclude the patient will need to be repeated.

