7.8 Sensitivity Analysis

Sensitivity analyses will be undertaken for calculation of the primary endpoint in order to evaluate the robustness of the analysis. Of specific note, OS sensitivity analyses will be performed in the following subgroups of the ITT population:

- Per protocol population

Other sensitivity analyses include:

- Defining survival time as the time from the date of study enrollment to the date of death due to disease
- Censoring patients that started additional anticancer therapy.

Further details can be found in the SAP.

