6.4. Treatment Duration

Each cycle is 14 days, with Days 6, 7, 13, and 14 being rest days for pegilodecakin. FOLFOX will be administered on Day 1 of each cycle. Patients randomized to the investigational combination treatment (pegilodecakin plus FOLFOX) ARM 1, after completion of up to 12 cycles of combination chemotherapy or if experiencing chemotherapy intolerance (as defined as Grade 3 or 4 non-hematologic toxicity that has not resolved to baseline in 28 days or Grade 4 hematologic toxicity that has not resolved to baseline in 28 days) may continue to receive maintenance pegilodecakin if the patient continues to receive clinical benefit (CR, PR, or stable disease [SD]). Patients will be treated until tumor progression by RECIST v.1.1. For ARM 2 (FOLFOX only) patients may receive FOLFOX for up to 12 cycles or 24 weeks or until tumor progression by RECISIT v.1.1 or until patients experience unacceptable toxicity, require palliative radiotherapy, withdraw consent, or their physician feels it is no longer in their best interest to continue on study treatments whichever occurs earlier.

To mitigate the chance of detecting false-progression (ie, pseudoprogression) early in the course of treatment on ARM 1 with pegilodecakin in combination with FOLFOX, patients whose scans show radiographic progression in the absence of clinical deterioration including worsening Eastern Cooperative Oncology Group (ECOG) Performance Status (PS) as assessed by the Investigator may remain on study treatments and should have an additional scan 4 weeks (±3 days) later as outlined in protocol Section 8.1.1. If this subsequent scan shows disease progression, the patient will be discontinued from study treatments.

7. General Statistical Considerations

7.1. Population:

The enrolled population includes all patients who sign the informed consent document.

The intent-to-treat (ITT) population includes all randomized patients per interactive voice response system (IVRS).

The safety population includes all randomized patients who received any amount of pegilodecakin or FOLFOX.

Per-Protocol Population: All patients who are in the safety population and have no major protocol deviations.

The major protocol deviations which will result in exclusion from the Per-Protocol population are listed below. This is not an exhausted list and may be amended over the course of the trial.

- patients with disease other than metastatic pancreatic adenocarcinoma
- patients with ECOG >1 at baseline

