10.1.4.1. Dose Reductions

Each drug component may be reduced. Number of patients with at least 1 dose reduction, reason for reductions, and number of dose reductions will be summarized for each treatment arm for

each component of treatment. Each FOLFOX dose reduction level is defined in protocol Table 12.

11. Efficacy Analysis

All efficacy analyses will be based on the ITT population.

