11.1. Primary Efficacy Analysis

The primary endpoint is OS. Overall survival is defined as the time from date of randomization to the date of death (due to any cause). For patients whose last known status is alive at the data cutoff date for the analysis, time will be censored as the last contact date prior to the data cutoff date.

The null (H_o) and alternative (H_a) hypotheses for testing overall survival are:

H_o: HR pegilodecakin + FOLFOX/FOLFOX alone = 1 H_a: HR pegilodecakin + FOLFOX/FOLFOX alone \neq 1 (superiority)

The hypotheses will be tested using a 2-sided stratified log-rank test. The stratification factors from IVRS will be used. Kaplan-Meier (K-M)estimates for the median time along with 95% CIs for each randomized arm; the hazard ratio with 95% CI will be provided as well.

Survival rates at fixed time points (3 months, 9 months, 12 months, 15 months, etc.) will be estimated using K-M estimate for each treatment group. These rates will be compared based on a normal approximation for the difference between the treatment arms. Associated 2-sided 95% CI will be calculated.

Hazard ratios for overall survival and their 95% CIs will be provided using Cox proportionalhazard model(Cox 1972) with treatment, stratification factors (from IVRS).

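### OS sensitivity analysis 2 is a cause-specific analysis labelled overall survival: non-disease deaths are censored without an attribution rule, and its start date is undefined

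*SAP*

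**What the plan says.** The primary endpoint is all-cause and runs from randomization. SAP 11.1: "Overall survival is defined as the time from date of randomization to the date of death (due to any cause").

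SAP 11.3.5 adds OS sensitivity analysis 2, "defining OS time as the time from the date of study enrollment to the date of death due to study disease". It then states: "For patients that have died due to reasons which are not disease related, survival time will be censored at the date of death". Protocol 7.8 lists the same start and event, "Defining survival time as the time from the date of study enrollment to the date of death due to disease", among analyses meant to test the robustness of the primary endpoint. It does not say how other deaths are handled.

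The start date is not defined. SAP 7.2 defines the dates of randomization and first dose, but no date of enrollment. SAP 7.1 says "The enrolled population includes all patients who sign the informed consent document", and SAP 8.1 splits that population into randomized and not randomized patients, so within the SAP enrollment comes before randomization. Protocol 3.1 points to a later moment: it lists enrollment as an "outcome of the screening process (eg, enrolled into study, reason for ineligibility, or refusal to participate").

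The population is set at the opening of SAP section 11: "All efficacy analyses will be based on the ITT population". Everyone analyzed was therefore alive at randomization.

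**The concern.** A sensitivity analysis of OS should test whether the all-cause result survives a change in assumptions. This one changes the question. It estimates the hazard of dying of pancreatic cancer, and a death from toxicity is handled as a censored observation. For an add-on treatment, non-disease death is one way in which a benefit could be offset, and here it drops out of the event count.

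Three features add to this:

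- The trial is open-label and relatedness is judged by the investigator (protocol 9.3), so the classification that decides which deaths count is made with the arm known.
- Neither document has a rule for attributing a death to disease, treatment or another cause in this analysis, and a death of unknown cause has no stated place. Protocol 9.1.1 says what to report as an SAE when progression is uncertain, but that is a reporting rule and is not linked to this analysis.
- The protocol expects added toxicity. Section 1.1.1 says the combination may bring additional adverse events. Section 1.2.5.1.1 reports treatment-related Grade 3 anemia in 11 of 25 pancreatic patients on FOLFOX plus 5 µg/kg, and Grade 3–4 thrombocytopenia in 55% with uninterrupted daily dosing, which the 5-days-on, 2-days-off schedule is predicted to avoid. These are not death rates.

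At stake is a favorable result being cited as support for OS without its counterpart. The different start date also means that its medians may not be comparable with the primary ones.

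**Working it through.** **Inputs.** From SAP 7.3: control median 5.9 months, experimental median 8 months, HR 5.9/8 = 0.7375, 393 deaths, 85% power, two-sided alpha 0.05, 1:1 allocation, 566 patients (283 per arm). From SAP 7.2: one month is 30.4375 days. From protocol 6.1 and Appendix A: consent and screening within 21 days before randomization. The shares of deaths that are not disease related, f1 in Arm 1 and f0 in Arm 2, are assumptions.

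**1. The plan's own figure.** Schoenfeld: 4 × (1.960 + 1.036)² / (ln 0.7375)² gives 388 deaths. Freedman: (1.960 + 1.036)² × (1.7375/0.2625)² gives 394. Power at 393 deaths is 0.855 with one look, and 0.849 with two looks at nominal levels 0.015 and 0.045. The 393 deaths are reproduced and none of what follows alters them.

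**2. Effect of the censoring.** With constant hazards, and each arm's share constant over time:

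- HR for disease death = all-cause HR × (1 − f1)/(1 − f0)
- HR for other death = all-cause HR × f1/f0
- Events left of 393, taking deaths as split equally between arms = 393 × (1 − (f1 + f0)/2)

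| Assumed f1 / f0 | Disease HR if all-cause HR is 1.00 | Other-death HR if all-cause HR is 1.00 | Disease HR if all-cause HR is 0.7375 | Events left |
|---|---|---|---|---|
| 5% / 5% | 1.000 | 1.0 | 0.7375 | 373 |
| 5% / 2% | 0.969 | 2.5 | 0.715 | 379 |
| 10% / 5% | 0.947 | 2.0 | 0.699 | 364 |
| 10% / 2% | 0.918 | 5.0 | 0.677 | 369 |

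Example for the second row: 1.00 × 0.95/0.98 = 0.969. The plan would report the disease column alone. The other-death column, which carries the opposite message, is not planned.

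**3. Effect of the start date, if enrollment means consent.** A lead time of d days adds d/30.4375 months to every time. At the full 21 days this is 21/30.4375 = 0.69 month, which is 11.7% of 5.9 months and 8.6% of 8 months. A constant shift leaves the difference in medians at 2.1 months.

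The effect on the HR was simulated: 400 trials, 283 per arm, uniform entry over 25 months, exponential survival, cut-off at 393 deaths, and a lead time drawn from 1 to 21 days with the same distribution in both arms. The mean Cox HR was 0.7355 from randomization and 0.7358 with the lead time, so it is unchanged for practical purposes.

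**The case against.** The strongest reply is that nothing important depends on this analysis. Primary OS counts every death. Analysis 2 is outside the testing hierarchy in SAP 11.4. Deaths are summarized by primary reason and period in the ITT population (SAP 12.1.4), and adverse events leading to death are listed (SAP 12.1). This stands, and it limits the point to one supportive analysis. But the summary and listings give no between-arm estimate to set beside a disease-specific HR.

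Second, censoring other deaths is how a cause-specific HR for disease death is ordinarily obtained. That also stands. The defects are the label, the missing companion estimate and the missing attribution rule.

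Third, reading enrollment as consent is an inference from a population definition, and protocol 3.1 points to a later time. This is correct. What is certain is that the date is undefined and is not stated to be randomization.

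Several stronger readings are tempting, and the documents do not support them:

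- A reader might infer that toxic deaths vanish from the trial's survival result. They remain in primary OS. In analysis 2 the patients contribute follow-up until death, and only their events are lost.
- A reader might infer that the consent-based clock favors AM0010. The interval precedes randomization and is balanced, so it lengthens both medians and leaves the HR alone.
- A reader might infer a much longer lead time from re-screening, since only "Patients who are re-screened after 30 days must be re-consented". But protocol 3.1.1 and 6.1 require the progression diagnosis and the scan showing it within 28 days before randomization, so a long gap after consent could not be typical of a whole arm.
- A reader might set a shifted HR against the boundaries in SAP Table JZGB.7.1. Those belong to all-cause OS, the final one at 393 deaths, and are stated to be for reference only. Analysis 2 would have fewer events.

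**Conclusion.** The point holds as one of labelling, definition and completeness. Analysis 2 is disease-specific survival under an OS label. Its HR moves toward AM0010 if non-disease deaths are a larger share of deaths in Arm 1, and a true HR of 1.00 would read 0.97 to 0.92 for assumed shares of 5%/2% to 10%/2%. With equal shares there is no shift; with a larger share in Arm 2 it would go the other way.

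The sizes rest on constant hazards and on assumed shares. The documents show added toxicity but give no rate of treatment-caused death, so they do not establish that a shift will occur.

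The start date is a separate and smaller defect: if it is consent, at most about 0.7 month on the medians at 21 days, with no change in the HR. The primary all-cause test, its alpha and its 393 deaths are unaffected.

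**What to change.** In SAP 11.3.5:

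- Start the clock at randomization, as for primary OS.
- Rename the analysis disease-specific survival, and stop presenting it as a robustness check of OS.
- Report cumulative incidence of disease death and of other death by arm, each treated as a competing event for the other, with the cause-specific HRs for both side by side. The disease-death HR will still censor other deaths; the companion HR keeps those deaths visible.
- Place treatment-related deaths in other death, and state how deaths of unknown cause are classed.

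Align protocol 7.8 with the same start, label and handling. The reason for death is already to be summarized under SAP 12.1.4, so the cost is SAP and protocol wording and one extra table, with no new data.

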11.3.6. Exploratory Tumor Marker Analyses

A separate analysis plan for tumor marker analyses will be provided.

11.4. Testing Hierarchy for Efficacy Endpoints

In order to preserve an overall 2-sided type-I error rate of 5%, a hierarchical testing approach (Glimm et al. 2010) will be applied to key secondary endpoints following analysis of the primary endpoint of OS. The hierarchical ordering of key secondary endpoints is as follows:

- 1. Progression-Free Survival
- 2. Objective Response Rate

If primary analysis of OS is statistically significant either in interim or final, then stratified logrank test for the PFS will be tested with a 2-sided type one error of 5%. If OS is not statistically significant. Progression-free survival and ORR will not be further tested. If PFS analysis is statistically significant, then ORR will be further tested with stratified CMH test with a 2-sided type 1 error of 5%. If any endpoint is not statistically significant, the following endpoints will not be further tested.

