7.4. Planned Interim Analyses/Final Analysis

Two interim analyses are planned for this study. The first interim analysis will be performed when approximately 60 randomized patients have had the opportunity to complete 4 months of therapy from the date of randomization. The nominal significance will be calculated based on O'Brien and Fleming alpha spending function in EAST v6.4. The second interim analysis is planned after approximately 276 deaths (70% of the 393 events) have been observed. The stopping boundaries will be derived based on the actual observed deaths at the first and second interim analysis. If the second interim analysis is performed approximately at 276 deaths, the study could be stopped by the DMC for efficacy if the p-value is <0.015. The nominal significance level for the final look at OS after 393 events would then be 0.045.

	Interim Analysis 1	Interim Analysis 2	Final Analysis
Conditions	Approximately 60 randomized patients who have had the opportunity to receive 4-months of therapy	Approximately 276 OS events	393 OS events
Alpha level	0.0001a	0.015	0.045
Upper HR Boundaries	2.145	1.342	1.224
Lower HR Boundaries	0.466	0.745	0.817

Table JZGB.7.1.Schedule of Analyses

Abbreviations: HR = hazard ratio; OS = overall survival.

^a A very small alpha is planned to be spent at the first interim analysis. Hazard Ratio boundaries are calculated based on the alpha spent. Hazard ratio (HR) boundaries are calculated based on the alpha spent. The O'Brien-Fleming (OBF) spending function is used to allocate the alpha at analysis 2 and final analysis with total alpha level of 0.0499. The actual alpha at each interim analysis will be recalculated based on the number of events observed at each analysis. The HR boundaries are for reference only and they are not for decision making.

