14.1. Interim Analysis

A planned first interim analysis will occur once at least 60 randomized patients who have the opportunity to receive 4 months of therapy from the date of randomization. The interim analysis is not designed to stop the study early for outstanding efficacy. Based on review of the PK exposure-safety and PK exposure-efficacy on the aggregated data of composite efficacy endpoints (PFS, ORR, and OS), the DMC will recommend continuing the Phase 3 trial, amending the study protocol, or stopping the study. The study will continue to enroll while this analysis is being completed.

A second interim analysis is planned when approximately 276 deaths (70%) of 393 deaths are reached in this event-driven trial. Details of the interim analysis results will be reviewed by the DMC. The DMC will inform the sponsor whether the interim efficacy boundary was met and provide the Sponsor with a recommendation to complete the trial as planned, modify, or discontinue the trial.

15. References

- Cox DR. Regression models and life-tables. J Royal Stat Soc Ser B. 1972;34(2):187-220.

Irwin JO. The standard error of an estimate of expectational life. J Hygiene. 1949;47;188-189.

- Karrison TG. Use of Irwin's restricted mean as an index for comparing survival in different treatment groups-- interpretation and power considerations. *Control Clin Trials*. 1997;18(2):151-167.

Leo Document ID = 1f124bc1-036e-4fe6-ab27-907d3eb67d37

Approver: PPD Approval Date & Time: 08-Apr-2019 00:38:08 GMT Signature meaning: Approved

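### SAP 11.4 tests PFS and ORR at a flat two-sided 5% at whichever look OS succeeds, with no per-look level and no retest rule, so the stated 5% is not assured

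*SAP*

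**What the plan says.** SAP 11.4 states its aim: "In order to preserve an overall 2-sided type-I error rate of 5%, a hierarchical testing approach" is applied to the key secondary endpoints, PFS first and then ORR. The gate is "If primary analysis of OS is statistically significant either in interim or final". Once it opens, "then stratified logrank test for the PFS will be tested with a 2-sided type one error of 5" per cent. If PFS succeeds, "then ORR will be further tested with stratified CMH test with a 2-sided type 1 error of 5" per cent. A failure at any step stops testing of the endpoints below it.

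For OS the levels differ by look. SAP 7.4 says "The second interim analysis is planned after approximately 276 deaths (70% of the 393 events) have been observed". At that look "the study could be stopped by the DMC for efficacy if the p-value is <0.015", and "The nominal significance level for the final look at OS after 393 events would then be 0.045". Table JZGB.7.1 and protocol Table 16 repeat these levels.

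Protocol 7.5.4 defers the PFS and ORR testing details to the SAP, so SAP 11.4 is the only rule. Neither document gives a spending function, a level per look or a retest rule for PFS or ORR.

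SAP 14.1 has the DMC tell the sponsor whether the efficacy boundary was met and "provide the Sponsor with a recommendation to complete the trial as planned, modify, or discontinue the trial".

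**The concern.** A hierarchy controls error in a fixed-sample trial when each step uses the full level. In a group-sequential trial the gate can open at more than one look, and two problems follow.

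- **Selection of the look.** PFS data at the second interim are incomplete, and a correlated endpoint (OS) decides whether PFS is read then or later. Even a single PFS test at 5% then need not have exactly 2.5% error on the benefit side.
- **A possible second test.** Crossing the OS boundary at the second interim permits stopping but does not require it. If the trial runs on, OS has already succeeded, and nothing bars testing PFS at 5% again with more events.

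PFS and ORR are the only secondary endpoints in the formal hierarchy, so their confirmatory claims rest on this paragraph.

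**Working it through.** **Inputs from the documents.** 276 and 393 deaths; OS levels 0.015 and 0.045; hazard ratio (HR) 0.7375; 85% power; two-sided 0.05 (SAP 7.3, 7.4). Enrolment of 25 months (protocol 2.3.4). Typical second-line median PFS of 3 months (protocol 1.1.1).

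**Assumptions.** OS-PFS correlation 0.3 to 0.9; uniform accrual; exponential times; PFS truly null. The 0.0001 spent at the first interim is ignored.

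**1. Reproduce the OS design.**
- Schoenfeld events: 4(1.960 + 1.036)² / (ln 0.7375)² = 35.91 / 0.0927, or 388. Freedman's formula gives 394. The stated figure is 393.
- Information fraction: t = 276/393 = 0.702. Lan-DeMets O'Brien-Fleming spending per tail is 2[1 − Φ(2.241/√0.702)] = 0.0075, so 0.0150 two-sided; the final level is then 0.0454. Both agree with the plan.
- The pair 0.015/0.045 gives an overall OS error of 0.0496, so OS is controlled.

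**2. PFS information at the second interim.** On these assumptions 276 deaths fall at about month 20 to 21, with about 450 to 473 of 566 patients enrolled. About 74% to 77% of the PFS events expected at 393 deaths would then be available. PFS information fractions f = 0.702 and 0.75 are used below.

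**3. Error formulas.** Let O₁, O₂ be the OS statistics and P₁, P₂ the PFS statistics at the two looks. Then corr(O₁,O₂) = √t, corr(P₁,P₂) = √f, c₁ = 2.432 and c₂ = 2.005.
- Tested once: P(O₁ ≥ c₁, |P₁| ≥ 1.96) + P(O₁ < c₁, O₂ ≥ c₂, |P₂| ≥ 1.96).
- Retested: P(O₁ ≥ c₁, and |P₁| or |P₂| ≥ 1.96) + the same second term.

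The benefit-side versions use P ≥ 1.96 in place of |P| ≥ 1.96.

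**4. Tested once.** Benefit-side error, maximised over the OS effect (nominal 2.5%):

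| Correlation | f = 0.702 | f = 0.75 |
|---|---|---|
| 0.3 | 2.54% | 2.53% |
| 0.5 | 2.61% | 2.58% |
| 0.7 | 2.75% | 2.70% |
| 0.9 | 3.08% | 2.99% |

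The value is about 3.7% as the correlation approaches 1. At the design HR it is 2.5% to 2.6%. The two-sided error never exceeded 5%.

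**5. Retested at 5%.** At the design HR the OS drift is −ln(0.7375)·√393/2 = 3.02, and OS crosses at the second interim with probability 0.54. Two-sided PFS error, from 4 million simulated draws per cell, shown as f = 0.702 / f = 0.75:

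| True OS HR | corr 0.3 | corr 0.5 | corr 0.7 | corr 0.9 |
|---|---|---|---|---|
| 0.7375 | 5.4% / 5.3% | 4.9% / 4.8% | 4.3% / 4.2% | 3.8% / 3.7% |
| 0.65 | 7.0% / 6.8% | 6.7% / 6.5% | 6.2% / 6.0% | 5.5% / 5.3% |
| 0.60 | 7.4% / 7.2% | 7.3% / 7.1% | 7.0% / 6.9% | 6.6% / 6.5% |

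As OS becomes certain to cross at the second interim, the error tends to 1 − P(|P₁| < 1.96, |P₂| < 1.96). This is 7.55% at f = 0.702, 7.34% at 0.75 and 6.48% at 0.90.

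**6. With per-look levels for PFS.** The same limit with 0.015/0.045 is 4.96% at f = 0.702, 4.87% at 0.75 and 4.59% at 0.90, retest included. An equal-level boundary needs about 0.032 per look at f = 0.70 and 0.033 at 0.75.

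**The case against.** The strongest reply is that the SAP promises only a two-sided 5%, and one test at the look where OS succeeds delivers it. The 2.5% benefit-side standard is not written into the plan for PFS or ORR. This stands as far as it goes. The two-sided total stays within 5% partly because, with positive correlation, an OS success makes harm-side PFS rejections rare. The direction in which a claim would be made still runs above 2.5%.

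Second, no retest is specified. The list of DMC recommendations in SAP 14.1 is generic, covers met and unmet boundaries alike, and does not mention PFS or ORR. A reader might infer that the plan intends two PFS tests, or that its PFS error is 7.5%. The documents support neither: the retest is only not excluded, and the high figures need PFS null together with an OS effect well beyond the design. The rule against testing endpoints below a failed one governs order within the hierarchy and does not settle a repeat of the failed endpoint.

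Third, the 5% could mean a total to be spent across looks, since SAP 11.4 cites a paper on hierarchical testing in group-sequential trials. That is arguable, but the per-look levels needed to apply it are absent.

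Finally, ORR was not computed. It depends on evaluable patients rather than PFS events and is reached only after PFS succeeds.

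**Conclusion.** The gap is real and of moderate size. SAP 11.4 assigns a flat 5% at either look without a per-look level or a retest rule.

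- **Tested once:** the stated two-sided 5% holds, with a modest benefit-side PFS excess of about 2.6% to 3.1% for correlations 0.5 to 0.9 in the worst case over the OS effect.
- **Retested at 5%:** the two-sided error is about 4% to 5% at HR 0.7375 for correlations 0.5 to 0.9 and slightly above 5% at correlation 0.3. It can reach about 7.2% to 7.5% when the OS effect is much stronger than designed.

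The stated 5% therefore depends on a rule that the plan does not contain. It would be wrong to infer that the error is inflated beyond 5% on every reading, or that OS is affected: the OS levels total 0.0496. The sizes rest on the joint-normal model, the assumed correlations and the projected PFS information. They apply to PFS only; for ORR the omission is the same but its size is not established.

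**What to change.** In SAP 11.4, replace the flat 5% with a pre-specified group-sequential boundary for PFS and for ORR. State the level at each look, and state whether an endpoint that fails at the second interim is tested again at the final analysis.

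O'Brien-Fleming-type levels of 0.015 at the second interim and 0.045 at the final, recalculated for the actual information, keep PFS at or below 5% even with a retest. An equal-level boundary of about 0.032 per look is an acceptable alternative. A sentence limiting each endpoint to one test would secure the two-sided 5% but would leave the benefit-side excess.

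The cost is one paragraph, settled before results by arm are seen, and some loss of PFS and ORR power at the second interim, where the critical value rises from 1.96 to 2.43 (or to about 2.14 with equal levels). The power loss cannot be quantified because the documents give no design effect for PFS or ORR.
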